6.3.3 Sensitivity analyses

As sensitivity analysis, we will do an available case analysis of the primary outcome, using the full analysis patient set. No further sensitivity analyses will be performed by CTU Bern.

CTU Bern	SAP for: ESTxENDS	Version: 1.0
----------	-------------------	--------------

CTU Bern	Template: Statistical Analysis Plan (SAP)	Version: 03
	Code: CS_STA_TEM-11	Valid from: 28.02.2019

6.3.4 Subgroup analyses

No subgroup analyses are planned to be performed by CTU Bern.

6.3.5 Additional analyses

No further analyses are planned to be performed by CTU Bern.

6.3.6 Assessment of statistical assumptions

To test model assumptions for continuous secondary outcomes, we will visually check residuals in QQ-plots and residual versus fitted plots.

If model assumptions are violated, transformation of the outcome (e.g. log-transformation), more robust methods (e.g. robust standard errors or robust regression) or non-parametric methods (i.e. Wilcoxon rank-sum test) will be considered.

6.4 Interim analyses

No interim analysis is planned

6.5 Missing data

Missing values in the primary outcome will be categorized as persistent smokers. We intend to obtain full follow-up data on all randomized participants.

Missing data in secondary smoking cessation outcomes will be treated as the primary outcome. If more than 5% of data is missing, all other secondary outcomes will be imputed, assuming values to be missing at random. Each outcome will be imputed separately to ensure robust imputation models. We will use all baseline variables (see Table 2) and outcome measures at all time points as predictors in the imputation models. The two intervention groups will be imputed separately. Variables with more than 50% missing values will not be used for the imputation model. Binary variables with a frequency of less than 5% in one category will be omitted from the predictors, levels of categorical variables with a frequency of less than 5% in one category will be combined with another level in a sensible way. Continuous variables will be log-transformed if it improves normality (checked by Shapiro-Wilks test and QQ plots). If predictors are too highly correlated among each other, we will only consider the predictor which is more strongly correlated with the outcome. We will use multiple imputation by chained equation. We will impute values using predictive mean matching for continuous and ordinal variables, logistic regression for binary variables, and a multinomial regression model for categorical variables with more than two levels. In total, fifty imputed data sets will be generated, which will be analysed as described using Rubin's rules (Rubin 1987).

CTU Bern	SAP for: ESTxENDS	Version: 1.0	
-----------------	-------------------	--------------	--

CTU Bern	Template: Statistical Analysis Plan (SAP)	Version: 03	
	Code: CS_STA_TEM-11	Valid from: 28.02.2019	Page 24 of 27

6.6 Safety evaluation

Safety outcomes will be analysed using the ITT and PP set.

The safety analysis will list the number of patients dropping out for both treatment arms, including the reasons, and a list of events for patients dropping out, with the treatment group, relation, grade, type of AE and potential free text.

AEs and SAEs will be summarized by presenting for both treatment arms the number of any AE, any SAE, and the number and percentage of patients with any AE or any SAE.

Further, we will present the

- grade and relation of AEs and SAEs (number of patients with events and the number of events),
- category and grade of AEs and SAEs
- category and relation of AEs and SAEs
- AEs and SAEs stratified by consumption (cigarettes, ENDS, both, none)

6.7 Subproject

Subprojects and further outcomes of interest are registered in clinicaltrials.gov under separate registration numbers. These subprojects and outcomes are not part of the current SAP, nor will they be analysed by CTU Bern.

6.8 Statistical software

All analyses will be done using the current version of Stata (StataCorp. 2019 Stata Statistical Software: Release 16. College Station, TX: StataCorp LLC.). The version of Stata and all used packages will be listed in the statistical report.

6.9 Quality control

The primary analysis of the primary and secondary outcomes will be double programmed by a second, unblinded statistician.

7. Changes from the protocol

The SAP is consistent with principle features of the statistical methods described in the protocol. The SAP only describes the primary and secondary analysis of primary and secondary outcomes. Any deviation from the protocol is detailed hereunder with reason. Further analysis of these outcomes, as well

CTU Bern	SAP for: ESTxENDS	Version: 1.0	
CTU Bern	Template: Statistical Analysis Plan (SAP)	Version: 03	
	Code: CS_STA_TEM-11	Valid from: 28.02.2019	Page 25 of 27

as for additional outcomes are planned by the PI and described in the protocol, but will not be further specified in this SAP.

Table 4: Changes from protocol

Header	Change	Reason
6.1 Outcome definitions	This SAP only focuses on the primary outcome for the main analysis at 6-month follow-up. The primary outcome for the extended follow-ups at 12- and 24-months is not part of this SAP.	Initial outcome defined in the initial protocol was at 6-month follow-up.

CTU Bern	SAP for: ESTxENDS	Version: 1.0
-----------------	-------------------	--------------

CTU Bern	Template: Statistical Analysis Plan (SAP)	Version: 03
	Code: CS_STA_TEM-11	Valid from: 28.02.2019

8. References

Estimands and SOPs

European Medicines Agency, Committee for Human Medicinal Products; Draft ICH E9 (R1) addendum on estimands and sensitivity analysis in clinical trials to the guideline on statistical principles for clinical trials, step 2b - Revision 1. 30 August 2017.

SOP Data preparation and programming, CS_STA_SOP_05, version 04, 11.09.2018

SOP Statistical data validation, CS_STA_SOP_02, version 03, 11.09.2018

References

StataCorp. 2019. *Stata Statistical Software: Release 16*. College Station, TX: StataCorp LLC.

CTU Bern	SAP for: ESTxENDS	Version: 1.0	
CTU Bern	Template: Statistical Analysis Plan (SAP)	Version: 03	
	Code: CS_STA_TEM-11	Valid from: 28.02.2019	Page 27 of 27

Statistical Analysis Plan (SAP)

Efficacy, Safety and Toxicology of Electronic Nicotine Delivery Systems as an aid for smoking cessation: The ESTxENDS multicentre randomized controlled trial

ESTxENDS

Administrative Information

Project number:	746
Trial registration number:	Swiss National Science Foundation # 173552 Clinicaltrials.gov: NCT03589989 (primary outcome). Further outcomes are registered separately, but not part of this SAP.

1.1 Background and rationale

Cigarette smoking is the leading cause of preventable death in Switzerland. Recently, electronic nicotine delivery systems (ENDS or vaporizers, also called e-cigarettes) have become popular with smokers who want to switch from tobacco cigarettes to ENDS to reduce their exposure to toxic compounds or to stop smoking. Only three rigorous RCTs have been published so far. They have promising, yet inconclusive results, as they were based on small samples. The safety and potential adverse effects of ENDS are also largely unknown. While the aerosol the users inhale appears safe in laboratory conditions, the difference in exposure to toxins (such as measures of exposure to organic compounds) and effect of toxins on the body (measures of oxidative stress) between smokers who quit (with or without ENDS) and those who use ENDS for a long time have not yet been assessed in an RCT.

1.2 Objectives

Test ENDS on:

- 1) the efficacy for cigarette smoking cessation and in reducing the number of cigarettes smoked over 6 months of follow-up;
- 2) the safety of ENDS
- 3) the effect of ENDS on exposure to inhaled toxic compounds;
- 4) the effect of ENDS on health-related outcomes (such as blood pressure, weight and respiratory symptoms).

2. Study methods

2.1 Trial design

The ESTxENDS trial is a multicentre, pragmatic, open-label randomized controlled trial with two parallel groups allocated in a 1:1 ratio. The trial will assess superiority of Electronic Nicotine Delivery Systems (ENDS) + standard of care (SOC) for smoking cessation to SOC alone in adult (≥ 18 years) smokers. The intervention group will receive free ENDS and nicotine-containing e-liquids to use ad libitum, plus SOC. The control group will receive SOC only.

2.2 Randomization

Simple randomization in a 1:1 ratio to the two arms.

CTU Bern	SAP for: ESTxENDS	Version: 1-02.0	
CTU Bern	Template: Statistical Analysis Plan (SAP)	Version: 03	
	Code: CS_STA_TEM-11	Valid from: 28-02-2019 to 06.2023	Page 6 of 27

2.3 Sample size

Details on the sample size calculation can be found in the protocol in section 11.2. In short, the sample size is based on the primary outcome, that providing smokers with ENDS and SOC leads to a higher rate of smokers who quit than usual care. Sample size was calculated for a 2-sided alpha of 0.05 and a power of 90%. Accounting for 5% drop-out, the sample size of the trial was defined to be 1172 smokers, 586 in both groups.

2.4 Framework

The trial will assess superiority of ENDS + SOC for smoking cessation to SOC alone in adult (≥ 18 years) smokers.

2.5 Statistical interim analyses and stopping guidance

Not applicable as no formal interim analysis is planned.

2.6 Timing of final analysis

All outcomes will be analysed collectively after 6 months of follow-up, once all 6-month follow-up activities are completed, all data is entered in the database, and all data is statistically validated and cleaned in the database. Before starting the analysis a final database export will be done.

2.7 Timing of outcome assessments

Study visits are scheduled at baseline and at 6 months (180 days – 4 weeks / + 12 weeks). Telephone visits are scheduled at target quit date (Day 0), Week 1 (7 ± 2 days), Week 2 (14 ± 3 days), Week 4 (28 ± 4 days), and Week 8 (56 ± 7 days).

The primary outcome is assessed at month 6 and needs to be derived from all telephone visits as well as the month 6 follow-up visit.

Secondary outcomes are assessed at months 6.

Further, outcomes are assessed at 12, and 24 months. These outcomes are not part of the current SAP.

2.8 Blinding

Participants, nurses and investigators will not be blinded. The laboratory personnel will be blinded for the determination of all urinary metabolites of nicotine (anabasine, cotinine, nornicotine, 3-OH cotinine). Any adverse event occurred in this study that generated care by a physician will be verified by a blinded external committee whenever possible. ~~The statistician who authors this SAP and performs the blinded~~

CTU Bern	SAP for: ESTxENDS	Version: 1-02.0
----------	-------------------	---------------------------------

CTU Bern	Template: Statistical Analysis Plan (SAP)	Version: 03	
	Code: CS_STA_TEM-11	Valid from: 28-02-2019 5.6.2023	Page 7 of 27

~~primary ITT and secondary per-protocol analysis of the primary and secondary smoking cessation outcomes will be blinded.~~ All ~~other~~ statisticians and data managers will not be blinded. The laboratory personnel will not be blinded for further urinary measures of exposures such as metabolites of polycyclic aromatic hydrocarbons (PAHs), of VOCs, creatinine and metabolites of TSNAs (NNAL, NNN, NNK).

There will be an automatic import of these urinary lab values into the database, programmed by a CTU data manager. Specific procedure and time points will be defined.

~~Breaking the blind:~~

~~The blinded statistician will be unblinded when all outcomes with blinding of the primary analysis are completely analysed. An unblinded statistician will have to download and label the data and prepare the analysis sets for the blinded analysis.~~

CTU Bern	SAP for: ESTxENDS	Version: 1.02.0	
CTU Bern	Template: Statistical Analysis Plan (SAP)	Version: 03	
	Code: CS_STA_TEM-11	Valid from: 28.02.2019 5.6.2023	Page 8 of 27

3. Data management

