6.2.2 Blinding procedures

Participants, nurses and investigators will not be blinded. We will blind both the statisticians who perform the main analyses and the laboratory personnel who determine urinary cotinine, anabasine, VOCs, TSNA (NNN, NNK and its metabolite NNAL) and PAHs (1- and 2-Naphtol and 1-OHP) levels.

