9.2 Assessments of outcomes

Participants will be seen in a healthcare facility in each center four times, at baseline, after 6-, 12- and 24- months. Data will be collected by study nurses, supervised by the responsible investigator at each site, based on protocols standardized across sites. All data will be directly collected via centralized computerized data entry forms. Laboratory analyses of urine samples will be centralized at the laboratory in Lausanne (Unisanté, Centre universitaire de médecine générale et santé publique, Lausanne). The laboratory is accredited ISO 17025 for nicotine quantification in urine, VOCs quantification, and it will use validated methods for the other compounds in urine and oxidative stress analyses. The samples are only stored and continued to be used with the participants consent independent from the study (see section 12.6). The blood samples from which analysis of blood lipids, HbA1c (only for participants with diabetes), creatinine will be performed, will remain in the main laboratory of each health center. The other blood sample for the analyses of inflammatory biomarkers from the centers in St. Gallen and Bern will be transported and stored in the biobank in Bern. Blood samples from participants in Geneva are stored at the local biobank in Geneva. Analyses of exhaled breath condensates will only be performed in Lausanne and thus centralized at the laboratory in Lausanne (Unisanté, Centre universitaire de médecine générale et santé publique, Lausanne). CTU Bern personnel will monitor quality. We will inform participants that some random phone calls will be recorded for quality monitoring. Quality monitoring will include reviewing calibration procedures for carbon monoxide (CO) and blood pressure measuring devices, weight and height scales.

The table below shows which outcome markers listed in 9.1 are collected in which center:

Tobacco use (questionnaires)	Bern, Geneva, Lausanne, St. Gallen, Zürich
Estimated ENDS use (ml e-liquids used)	Bern, Geneva, Lausanne, St. Gallen, Zürich
Exhaled CO	Bern, Geneva, Lausanne, St. Gallen, Zürich
Urinary nicotine, cotinine, anabasine	Bern, Geneva, Lausanne, St. Gallen, Zürich

Urinary metabolites of nitrosamines (TSNAs)	Bern, Geneva, Lausanne, St. Gallen, Zürich
Adverse events, serious adverse events	Bern, Geneva, Lausanne, St. Gallen, Zürich
VOC and PAH metabolites in urine	Bern, Geneva, Lausanne, St. Gallen, Zürich

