9.2.2 Assessment of secondary outcomes

The secondary outcomes will be measured as described for the primary endpoint.

Secondary smoking cessation outcome will be measured with a self-reported 7-day point prevalence abstinence (not having smoked cigarettes within the preceding week), again confirmed by urinary level of anabasine, and change in the self-reported number of cigarettes smoked per day (CPD) with 50% reduction in CPD from baseline to follow-up considered as successful reduction, measured as above.

For alternate validation methods of the primary and secondary outcomes, we will use CO-levels, which will be measured with a Micro Smokerlyser®; Bedfont Scientific Ltd.

Respiratory symptoms will be assessed by questionnaires:

- COPD Assessment Test (CAT), Modified Medical Research Council (MMRC) Scale, Asthma Test (ACT/ ECRHS)

Each Urine sample will be split into six aliquots to quantify cotinine and anabasine (see above), PAH metabolites, VOCs, propylene glycol, TSNAs, 8-OHdG and 8-isoprostanes, since no analytical method can measure all the compounds together. The different compounds will be estimated as follows:

- Concentrations of urinary cotinine and anabasine, VOCs, TSNAs and PAHs will be measured
- Oxidative stress will be assessed by quantifying 8-OHdG and 8-isoprostane concentrations in both EBC and urine
- We will adapt the method for analyzing urinary TSNAs from Xia et al.³⁰ After enzymatic hydrolysis with a β -glucuronidase solution, the urine sample will be extracted using solid phase extraction (SPE) columns, and analyzed by LC/MS/MS.
- We will use a high performance liquid chromatography (HPLC) method developed by the IST laboratory to analyze PAHs (1- and 2-Naphthol and urinary 1-OHP).

Exhaled breath condensates (EBC) other than CO will be performed in all participants at the Lausanne site during the first as well as the outcome visit (baseline and 6 months), based on guidelines from the American Thoracic Society (ATS)/European Respiratory Society (ERS) Task Force for EBC collection⁸⁷. EBC will be sampled with an EcoScreen II system (total exhaled volume of about 120 L). After collection, each sample will be aliquoted. To avoid auto-oxidation of fatty acids (potential impact on 8-isoprostane levels), we will add tert-butyl hydroxytoluene and rapidly freeze the sample. The samples will be stored at -70°C for a maximum of 1 month.⁹⁰

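### SAP 2.0 leaves laboratory staff unblinded for NNAL, other TSNAs, PAHs, VOCs and creatinine, against the protocol's laboratory blind and without declaring it

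*Supplement*

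**What the plan says.** Protocol 9.0, section 6.2.2: "We will blind both the statisticians who perform the main analyses and the laboratory personnel who determine urinary cotinine, anabasine, VOCs". The same sentence goes on to the TSNAs and ends with "NNK and its metabolite NNAL) and PAHs (1- and 2-Naphtol and 1-OHP) levels". Section 6.1 adds, without limit to any analyte, that laboratory personnel are blinded to allocation, and describes the biochemical verification as blinded.

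SAP 2.0, section 2.8, splits the laboratory blind in two. For nicotine metabolites it keeps it: "The laboratory personnel will be blinded for the determination of all urinary metabolites of nicotine", with anabasine and cotinine named. For the rest it does not: "The laboratory personnel will not be blinded for further urinary measures of exposures", followed by a list of PAHs, VOCs, creatinine and the TSNAs (NNAL, NNN, NNK).

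On sample handling, protocol 9.2 says "Laboratory analyses of urine samples will be centralized at the laboratory in Lausanne", and protocol 9.2.2 says "Each Urine sample will be split into six aliquots to quantify cotinine and anabasine" and the other analytes listed there.

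SAP section 7 claims consistency with the main features of the protocol's methods and says that deviations are set out with reasons in Table 4. The one blinding row there concerns the statistical analyses. The change note that closes the SAP is also silent on the laboratory.

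**The concern.** The trial is open label for participants, nurses and investigators, and SAP 2.0 now unblinds all statisticians as well. For the efficacy outcomes the laboratory is therefore the only masked step left.

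NNAL matters for cessation as well as for toxicology. It decides quitter or smoker in four secondary cessation outcomes, and a missing NNAL value switches validation to anabasine or CO. Re-runs, readings close to the cut-off and rejected samples can therefore change a participant's status. If staff know the arm, those decisions can differ between arms. SAP Table 3 writes the NNAL cut-off with a creatinine term, so creatinine may bear on the same classification. For the TSNA, VOC and PAH concentrations, the measured value is itself the outcome.

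**Working it through.** The core of this check is a comparison of texts.

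**1. Blinding status by analyte**

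| Analyte | Protocol 9.0 | SAP 2.0, 2.8 |
|---|---|---|
| Anabasine, cotinine | blinded (6.2.2) | blinded |
| NNAL, NNN, NNK | blinded (6.2.2) | not blinded |
| VOCs | blinded (6.2.2) | not blinded |
| PAHs | blinded (6.2.2) | not blinded |
| Creatinine | blinded only through the general sentence in 6.1 | not blinded |

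The documents agree in the first row and conflict in the other four.

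**2. Is it a declared change?** SAP 1.0 (June 2020) already carried the sentence. Protocol 9.0 (July 2021) still stated the full laboratory blind. SAP 2.0 (June 2023) edited this same paragraph to remove the blinded statistician and left the laboratory sentence in place. Table 4, the closing note and the protocol's history of changes give no reason for it.

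**3. Cessation outcomes affected.** SAP 6.1 lists these binary abstinence outcomes as secondary:
- continuous abstinence: NNAL (1 outcome, 1 with NNAL);
- 2-week grace period: self-report, anabasine, NNAL (3, 1 with NNAL);
- up to 5 cigarettes: self-report, anabasine, NNAL (3, 1 with NNAL);
- 7-day point prevalence: self-report, anabasine, NNAL (3, 1 with NNAL).

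Total: 1 + 3 + 3 + 3 = 10, of which 1 + 1 + 1 + 1 = 4 use NNAL first.

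**4. Concentration outcomes.** Protocol 5.2 lists TSNAs, VOCs and PAHs as secondary outcomes. They are not among the core outcomes of SAP 2.0, so this part rests on the protocol.

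**5. Scale, as a what-if only.** The documents give no misclassification rate. Assume no true difference, n = 586 per arm, a validated quit rate p of 12% (the planned control rate) or 19% (the planned intervention rate) in both arms, and a reading shift δ in one arm only. The false-positive rate of the two-sided 5% test is then

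Φ((δ − 1.96·SE0)/SE1) + Φ((−δ − 1.96·SE0)/SE1),

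where SE0 = √(2p̄(1−p̄)/n), p̄ = p + δ/2 and SE1 = √([p(1−p) + (p+δ)(1−p−δ)]/n).

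| δ (points) | participants (δ × 586) | p = 12% | p = 19% |
|---|---|---|---|
| 0 | 0 | 5.0% | 5.0% |
| 0.5 | 2.9 | 5.8% | 5.5% |
| 1 | 5.9 | 8.1% | 7.2% |
| 2 | 11.7 | 17.4% | 13.7% |
| 3 | 17.6 | 32.4% | 24.6% |

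At 12%, about 70 participants per arm would be validated quitters (0.12 × 586 = 70.3). A 1-point shift then means that about 6 in 70, or 9%, move the same way in one arm only. Nothing in the documents shows a shift of any size. The table applies to an NNAL-validated outcome, not to the primary outcome.

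**The case against.** Four counter-arguments have weight.

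- **The assays leave little room for judgement.** TSNAs are measured by LC/MS/MS and PAHs by HPLC, the laboratory uses validated methods, and values enter the database automatically. Each NNAL-validated outcome also requires self-reported abstinence, so the laboratory can change the status only of people who say they have quit. This stands, and it limits the size. It does not reconcile the two texts, and automatic import protects the transfer of a value rather than its reading.
- **Not blinded need not mean that staff are told the arm.** Protocol 12.5 uses random participant codes that do not encode allocation, and section 7.3 restricts the randomization lists to system administrators. This also stands. The documents do not show that the laboratory received allocation, only that the SAP no longer promises that it will not.
- **The primary outcome has its own stated blind.** A reader might infer that the anabasine blind fails because one laboratory handles aliquots of the same sample. The documents do not support that: SAP 2.8 says anabasine is measured blind, and nothing says that the same staff run both assays or that samples carry an arm label. What can be said is that no separation of staff, codes or assay order is described.
- **Scope.** A reader might extend the protocol 6.2.2 rule to exhaled breath condensate and creatinine, or picture a separate creatinine aliquot. Section 6.2.2 names neither, and the analytes listed for the aliquots in section 9.2.2 do not include creatinine.

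**Conclusion.** The contradiction is certain. It stands in the latest versions and is undeclared. It exposes 4 of the 10 binary abstinence outcomes in SAP 6.1, and the TSNA, VOC and PAH outcomes of the protocol, to detection bias that costs little to avoid. The direction and size of any bias are unknown, and it is probably small for the reasons given above. The primary outcome is not shown to be affected; for anabasine the gap is only a missing description of how the blind is kept.

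This rests on reading SAP 2.8 as the rule the laboratory would follow. The documents do not say which rule was applied in practice or when the assays were run.

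**What to change.** If assays are still to be run, replace the sentence in SAP 2.8 with the protocol rule: all urinary analytes, creatinine included, are measured on coded samples that carry no allocation or ENDS-use data. Add one line on how the anabasine blind is protected when aliquots of one sample are in the same laboratory. The cost is wording and sample coding. Nothing in the documents suggests that any assay needs the allocation.

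SAP 2.0 (June 2023) postdates the planned last participant out (05/22), and its closing note describes the analyses as done, so some or all assays may already have been run. In that case deleting the sentence could remove an accurate disclosure. Instead:
- record the deviation in Table 4 with its reason and the analytes or batches affected;
- state how the anabasine blind was kept;
- label the four NNAL-validated outcomes, and the TSNA, VOC and PAH results, as not laboratory-blinded.

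The cost is then a disclosure that makes the NNAL-validated results look slightly less favourable.
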